Once results have been analyzed, it is the intention of the research team to publish results and give public presentations about the aggregate outcomes of the study. All participants will be notified of publications stemming from the research as well as any public presentations on the UC Davis campus.

23) Setting

The orientation, questionnaire answering, and technology training will be conducted at a specified location at the participating clinics, where the patient obtains their routine care. There are numerous small and large conference rooms available to conduct all aspects of the intervention orientation and testing. Nurse health coaching sessions will be conducted over the phone, at times convenient to the participant.

24) Resources Available

Appropriate resources and funding are in place to conduct this study. Questionnaire administration and technology orientation will occur in-person at the clinic in which the participant receives their primary care services (see #23 above).

Personnel include:

PI and Co-Investigators: Responsible for overseeing the various aspects of the project: technology, recruitment, required training, nurse coaching, data analysis, data safety and management, IRB compliance, etc.

Health Coach: certified in Motivational Interviewing (MI) and trained to conduct initial intake and ~15 hours/week of health coaching and study administration. The Health Coach will have previous experience coordinating research trials and familiar with UCD IRB requirements.

Project Manager: The Project Manager has previous experience coordinating research trials and familiar with UCD IRB requirements. She will participate in recruiting subjects, screening, consenting, scheduling, and communicating along with the preparation and conduction of research procedures.

Junior Specialist: Will be supervised by one of the Co-investigators. The Jr. Specialist will be involved in scheduling orientations, procuring rooms for activities, recruitment, and data collection as well as providing technology on-boarding for participants and on-going technical support. He/She is familiar with UCD IRB requirements.

Patient Advisory Board Members: As part of the PCORI funding expectations, this project includes three Advisory groups: Patients, Providers and Technical/Computer Experts. The Patient Advisory Board provides input and guidance to the study team about study design, measures, recruitment strategies, and will assist in interpreting deidentified data. Several patient advisors have indicated interest in assisting with recruitment, and have offered to go to clinics to help recruit participants. Those interested will complete CITI training and will receive all appropriate training as members of the research team, and will be added to the research personnel list, before engaging in any direct contact with participants or data. We anticipate, with increased advertising of this project, we can enroll 30 participants a month. This means total enrollment would take approximately 6 months.

Significant research staff time will be devoted to conducting this research. The Project Manager has 75% time devoted to the execution, completion, and analysis of this research. Two health coaches will be hired at 75% time over a 12 month period to accommodate the extent of health coaching required during a rolling enrollment over 6 months.

25) Prior Approvals

n/a

26) Provisions to Protect the Privacy Interests of Subjects

The study staff will offer detailed explanation of the study to subjects prior to consent. It will be emphasized that all of the data collected in the study will be de-identified. All results will be analyzed in aggregate. It will be stored in a secure server and used expressly in de-identified form exclusively for the purposes of the aims of this research project.

Following consent, participants will be randomized and receive a study identification number. This number will be entered into the secure REDCap database on a tablet. The participant will be offered the questionnaire on either the tablet with their unique study identification shown at top. Their name and other unique identifiers will not be asked during the survey. If the participant would prefer to fill out the survey on paper, the same procedure will be followed and research staff will transcribe the survey into REDCap. Clinical and lifestyle (physical activity, nutrition, sleep) data will be stored in their clinical record (EPIC Hyperspace) which is HIPAA protected. Clinical data in their record may be viewed by their treating physicians and clinical team as part of standard care at UC Davis Health System. Including this lifestyle data in the clinical record will promote a wellness conversation and foster collaboration between diabetes patients and primary care providers.

All data stored by UC Davis researchers will have all personal identifiers removed and labeled with participant's study identification number. All electronic data will be stored on a password protected server that is accessed only by study personnel. All paper data will be stored in locked cabinets in a room with access limited to research personnel.

27) Compensation for Research-Related Injury

This research involves only minimal risk to subjects.

In the event a patient suffers an injury as a result of participating in this research study, the University of California will provide necessary medical treatment. Depending on the circumstances, the costs of the treatment may be covered by University or the study

Patient and Provider Engagement and Empowerment through Technology $(P^2E^2T^2)$ to Improve Health in Diabetes

sponsor or may be billed to the patient's insurance company just like other medical costs. The University and the study sponsor do not normally provide any other form of compensation for injury.

28) Economic Burden to Subjects

There are no other monetary costs to participate in the study. All technology costs will be covered by the study except if a participant uses their personal smart-phone or computing technology to visualize data collected by the provided activity sensors. This cost is one that the participant was already incurring. If they do not have a personal computing device compatible with the sensor technology, one will be provided without cost for the duration of the study.

29) Consent Process

Patients who are interested to participate in the study or are referred by their primary care provider will receive an initial telephone call to conduct the pre-screening assessment (see attached document) to determine if they are eligible to participate in the study. If someone is determined to be eligible, an appointment will be scheduled to consent the patient. During the consent process, the study will be described to potential participants. A member of the research team will describe the study, what is required of the participant, study procedures and answer any questions the potential participants may have. If the subject would like to take time to consider participation, they will be offered an intake date in the near future.

Following consent using the Informed Consent Document (see attached), subjects are enrolled in the study and randomized into one of two study arms. Subjects will have the choice of receiving a hard copy of their signed consent form or receive the form by email. They will then be administered initial surveys.

A study telephone line is available to allow participants to reach the Project Manager with any concerns regarding ongoing consent or participation.

30) Process to Document Consent in Writing

The research team will follow the "SOP: Informed Consent Process for Research (HRP-090)" (attached) to consent participants.

31) Drugs or Devices

n/a

References

- 1. Dall, TM et al. (2010). The economic burden of diabetes. *Health Affairs* 29:297-303.
- 2. Narayan, KM et al. (2006). Impact of recent increase in incidence on future diabetes burden: U.S., 2005-2050. *Diabetes Care* 29:2114-6
- 3. Boyle, JP et al. (2001). Projection of diabetes burden through 2050: Impact of changing demography and disease prevalence in the U.S. *Diabetes Care* 24:1936-40

Patient and Provider Engagement and Empowerment through Technology $(P^2E^2T^2)$ to Improve Health in Diabetes

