Our hypothesis is that patients in the $P^2E^2T^2$ arm of the study will be more engaged in identifying and achieving health goals related to their diabetes and will achieve better health outcomes compared to patients receiving usual care.

We will achieve this project through the following Specific Aims:

- Specific Aim 1: To evaluate the effectiveness of the P²E²T² program on diabetes management as measured by the following outcomes: 1) quality of life (QOL); 2) self-efficacy; 3) readiness to change; and 4) clinically relevant outcomes.
- Specific Aim 2: Compare specific health and fitness outcomes of individuals participating in each study arm.

5) Background

Diabetes

Diabetes mellitus (DM) is a growing public health problem highly amenable to prevention and health promotion interventions. Over 26 million people are diagnosed with diabetes, and an estimated 79 million people have pre-diabetes (1). The incidence of DM in the United States is escalating at alarming rates and by 2050, 48.3 million people will be diagnosed with diabetes, an increase of 198% from 2005 (2, 3). Type-2 diabetes is the most common type of diabetes accounting for 80-95% of cases (2-4). DM is a major risk factor for vascular complications including heart disease and stroke, hypertension, blindness, lower limb amputations, lipid abnormalities and kidney disease (5-8).

Health Behavior and Disease

Physical inactivity, poor eating habits, obesity and smoking are common risk factors for multiple chronic diseases, including DM, and are associated with premature deaths in the United States (40% of premature deaths compared to other factors such as genetic predisposition (30%), social circumstances (15%), health care (10%), and environmental exposures (5%)) (9). Recent evidence suggests an association between sleep impairment and type-2 diabetes, where duration and quality of sleep were significant predictors of glycemic control, suggesting that interventions which address sleep quality may be of value in glycemic control and diabetes management (10-13). These connections between health behavior and disease outcomes indicate the importance of a patient-centered, proactive and evidence based approach to prioritizing and enacting behavioral choices (14).

Gaps in Traditional Management of Diabetes

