Practice alerts: With the approval of clinics and providers participating in the study, the informatics team may initiate pop-up practice alerts when a potentially eligible patient is in the clinic for an appointment. If the patient meets pre-set guidelines (over 18 years of age, diagnosis of Type 2 diabetes), an electronic alert in the EHR will appear that this patient may be eligible for a UC Davis Research study for the provider to review. The provider has an option of ignoring this alert or may briefly discuss that the patient may be eligible for a study and inquire if the patient would like further information. If the person requests further information, the provider clicks a button that will send information to the study coordinator, so that a member of the research team can call the participant or meet with them in person to discuss the study.

Advertisements: Participants will be recruited between January and August, 2016 through advertisements/flyers placed at participating clinics at local health systems. The flyers will provide information and describe the study as a Technology Enabled Support Program for Patients with Diabetes.

Health Management and Education: Trained study personnel may also promote recruitment for the trial by attending and describing the study to participants during diabetes education classes conducted at the UC Davis Center for Health Management & Education. The study will be presented as described and advertisements/flyers will be distributed. When study personnel are present, potential participants will be given the option to sign up to receive further information about the study. Participants may also be recruited directly through referral by local providers or Advisory Board Members.

Randomization will be conducted through computer generated randomization using REDCap data management system. This randomization will occur immediately following consent by computer generated randomization programming in Redcap. The participant will then be assigned a study ID number which will be used to track all of their activity within the study (questionnaires, fitness tests, coaching sessions). Only the study ID #, no personal identifiers, will be included on any of these study documents.

Patient and Provider Engagement and Empowerment through Technology $(P^2E^2T^2)$ to Improve Health in Diabetes

Copies of recruitment flyers; provider letters; and informed consent documents are attached to this document.

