9) Compensation to the Subjects

All subjects, regardless of treatment arm, will be given a health monitoring device at the end of the study. Upon completion of study questionnaire and their regularly scheduled visit with their primary care physician all participants will receive \$50 at baseline, 3 and 9 months. Those participants in the intervention $(P^2E^2T^2)$ arm will receive a health monitoring device at the beginning of the study; and those participants in the Care Coordination arm of the study will also receive a health monitoring device upon successful completion of all study questionnaires. If participants do not complete all aspects of the study, they will not receive the health monitoring sensor device. Each sensor device is worth approximately \$75.

10) Study Timelines

Each individual will be enrolled in the study for 9 months. Each participant will complete a study questionnaire at baseline, 3 months and 9 months. Estimated duration of the study completion is 24 months from start of enrollment (January 1^{st} , 2016 – December 31^{st} , 2017).

11) Study Endpoints

Outcomes to be evaluated include: i) Quality of Life (QOL) measures; ii) Self-efficacy; iii) Readiness to Change; and iv) Clinically Relevant Indicators (HgbA1C, HDL, LDL, triglycerides). All measures will be collected in both groups at the study timelines. At baseline (time of recruitment), all participants will be asked to complete the surveys and the care coordinator will request the primary care provider orders for the laboratory tests measuring the clinical indicators. The lab tests are routinely used to monitor diabetes management and are typically covered by insurance. Should the patient not have a payment source for the laboratory assays, the project will cover the cost of the laboratory tests. At 3 months and 9 months, surveys links will be sent by email to each participant along with a reminder to complete the laboratory work ordered by their provider. If not completed, reminder emails or phone calls may be made by the study team. The primary endpoints of the study are: baseline data; data at the completion of five sessions of support calls during the 3 months of the intervention; and data at 6 months after the end of the intervention (9 months after baseline).

12) **Procedures Involved**

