Historical data, such as completed lab work values as identified above (Study Endpoints section), will be gathered by querying the EHR for all participants involved in the study. This will be accomplished by working with the Health Informatics for research group, led by [name].

All data and data identifiers related to this study will be destroyed seven years after completion of the study. All data findings from the study will be presented as aggregate data with no individual subject identifiers.

Subjects will be using commercial off-the-shelf (COTS) sensors, smart phone applications, and web-based physical activity dashboard technologies. Participants must agree to use the sensors and applications required for data collection. If they are unwilling to use this sensor, they will not be able to participate. Immediately following consent and randomization into the "Care Coordination" and "P²E²T²" arms, project staff will assist participants with technology set-up, configuration, use, and ensure that subjects understand the commercial terms of service agreements, before they begin the trial. In order to further protect individual privacy, subjects in the P²E²T² arm may choose to share with their coach only portions of the data streams from their devices/apps. That is, subjects have the option to filter the data streams shared with their coach by time of day, and specific metric (i.e. steps counted, calories burned, etc.).

Variable	Measure	Data Collection		
v ar lable	Measure	Baseline	3 months	9 Months
Age, Gender,	Demographic Data Form	Х		
Race/Ethnicity, Education				
Level, Income Level and				
Insurance Type				
Specific Aim 1				
Focus Groups		Х	Х	Х
Specific Aim 2				
Self-Efficacy	Diabetes Empowerment Scale –	Х	X	Х
	Short Form (DES-SF)			
Readiness to Change	Readiness to Change Survey	Х	Х	Х
Clinical Indicators	Electronic health record	Х	Х	Х
(Abstracted)				
	Patient Health Questionnaire	Х	Х	Х
	depression scale-9 (PHQ-9)			
Quality of Life	Perceived Stress Scale (PSS)	Х	X	Х
Quality of Life	PROMIS Measures – Physical	Х	X	Х
	Function SF, Emotional Distress			
	SF, Sleep Disturbance			

15) Provisions to Monitor the Data to Ensure the Safety of Subjects

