Patient and Provider Engagement and Empowerment Through Technology Program to Improve Health in Diabetes

PI: [name]

January 11, 2019

NCT number: NCT02672176

Analytical and Statistical approaches

We will use Stata v15.0 (Stata Corp, College Stations Tx 2017) for all statistical analyses. Descriptive analysis will yield means/standard deviations for continuous variables and frequencies for categorical variables. We will examine distributions to determine whether data meets assumptions for planned statistical analyses. We will compare patient demographic and health-related characteristics between the individuals in the intervention group and the usual care group. We will compare continuous variables using a Student's t test or the Wilcoxon Signed-Rank test, and will compare categorical variables using the chi-squared test and Fisher's exact test, as appropriate. We will compare number of steps per week at baseline (Week 2) versus 3 months (Week 13), baseline versus 9 months (Week 37) and 3 months versus 9 months, using a paired t-test to evaluate the change in physical activity over time.

We will calculate change in outcomes over time as the difference between baseline and 3 months, and baseline and 9 months for diabetes self-efficacy scores, depression severity (PHQ-9), patient stress score, and PROMIS measures (Emotional distress anxiety, and physical functioning). We will use Student's t test to compare the change in outcome between usual care and intervention groups (Significance level: $p \le .05$).

In the primary analysis, we will estimate the difference over time in the effects of the intervention over usual care in the study participants. This is an intent to treat analysis, with the assumption that any dropouts are missing at random. We will also use an analytical method (Mixed model) which accounts for the missing data contributed by participants who dropped out from the study. Lastly, we will conduct a sensitivity analysis to determine whether there is a difference with regards to the significance of our findings when we exclude participants who drop out from the analysis. All participants, regardless of intervention completion, will be included in the intent to treat analysis.

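### Aim 2 promises a between-arm comparison of fitness, but no measure is designated as the fitness outcome and the only activity analysis, a paired t-test of steps, has no arm term

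*Protocol*

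**What the plan says.** **The aim.** Protocol Section 4, Specific Aim 2: "Compare specific health and fitness outcomes of individuals participating in each study arm". This is a comparison by randomised arm, and it covers fitness as well as health.

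**The endpoints.** Section 11 lists quality of life, self-efficacy, readiness to change and "iv) Clinically Relevant Indicators (HgbA1C, HDL, LDL, triglycerides", and adds that "All measures will be collected in both groups at the study timelines". The schedule table in Section 14 has rows for demographics, focus groups, self-efficacy, readiness to change, abstracted clinical indicators, PHQ-9, perceived stress and PROMIS short forms, including Physical Function. Steps and activity are not in it. The randomisation paragraph of Section 8 mentions "questionnaires, fitness tests, coaching sessions" as activities tracked by study ID. No fitness test is named, timed or analysed anywhere else.

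**The activity analysis.** The SAP states "We will compare number of steps per week at baseline (Week 2) versus 3 months (Week 13", then adds baseline against 9 months (Week 37) and 3 against 9 months, all by paired t-test. It does not say which arm or arms enter.

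**The sensors.** Section 9 says that the intervention "arm will receive a health monitoring device at the beginning of the study", whereas "those participants in the Care Coordination arm of the study will also receive a health monitoring device upon successful completion of all study questionnaires". Section 14 says, without limiting it to one arm, "Participants must agree to use the sensors and applications required for data collection".

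**The concern.** A paired t-test asks whether the same people changed between two weeks. Aim 2 asks whether the two arms differ. The first does not answer the second, because season, novelty of the device, regression to the mean and the effect of being observed all move steps over time without any effect of the program.

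Two things are at stake. First, the fitness part of a stated aim has no endpoint and no randomised test. Second, a significant step trend could be read as showing that the program raised activity, when the analysis has no control group. The self-efficacy comparison on which the trial was sized (Section 7) is not affected.

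**Working it through.** The plan states no figure for fitness or steps, so there is nothing to reproduce. The check is a comparison of the aim, the endpoints, the schedule and the analysis, followed by an illustration.

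**Step 1. Is there a fitness endpoint?** In the Section 11 list and the Section 14 table, the count of step, activity or performance-fitness measures is 0. The closest row is PROMIS Physical Function at baseline, 3 and 9 months, labelled quality of life. It sits in the block headed Specific Aim 2, but those headings do not follow the current aims: the table puts focus groups under Aim 1 and self-efficacy under Aim 2, while Section 4 puts self-efficacy under Aim 1. Its position therefore does not designate it as the fitness outcome.

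**Step 2. Is there a between-arm activity analysis?**

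| SAP analysis | Outcomes named | Arm contrast? |
|---|---|---|
| Paired t-tests | Steps, three week pairs | No (0 of 3) |
| t-test of change scores | Self-efficacy, PHQ-9, stress, PROMIS anxiety and physical functioning | Yes; steps not listed |
| Mixed model, group-by-time | Self-efficacy, depressive symptoms, perceived stress | Yes; steps and physical functioning not named |

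HbA1c and lipids, the health side of Aim 2, are not named in the SAP at all.

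**Step 3. Could usual care supply steps?** Under Section 9 the usual-care device comes after the last questionnaire, which is at 9 months, so there would be no usual-care steps at Weeks 2, 13 or 37. Of the 300 participants planned (150 per arm, Section 7), about 150 would then contribute no activity data. Sections 6 and 12 also describe sensors as part of the intervention. Against this, Section 14 describes technology set-up straight after randomisation and names both arms, and the mailed-letter paragraph of Section 8 mentions technology training for either arm. The documents do not settle the question, so the figure of 150 holds only under Section 9. Step 2 does not depend on the answer.

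**Step 4. Illustration of what a paired test can show.** Assume that the true arm difference is zero and that steps rise equally in both arms by δ standard deviations of change. The values of δ are assumptions; the documents give none. The chance of a significant two-sided paired test is about Φ(δ√n − 1.960), where n is the number of people tested. The values 100 and 150 are the per-arm sizes in Section 7.

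| δ | n = 100 | n = 150 |
|---|---|---|
| 0.1 | Φ(1.000 − 1.960) = 17% | Φ(1.225 − 1.960) = 23% |
| 0.2 | Φ(2.000 − 1.960) = 52% | Φ(2.449 − 1.960) = 69% |
| 0.3 | Φ(3.000 − 1.960) = 85% | Φ(3.674 − 1.960) = 96% |

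So the paired test can often be significant when the program has no effect on steps.

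For comparison, the standardised arm difference detectable with 80% power is (1.960 + 0.842)√(2/n), with n per arm: 2.802 × 0.1414 = 0.40 for 100, and 2.802 × 0.1155 = 0.32 for 150. This applies only if both arms supply steps.

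**The case against.** The strongest reply is that a randomised physical contrast is already planned. PROMIS Physical Function is scheduled in both arms at all three time points, and the SAP compares its change between arms. The SAP also says that primary and secondary outcomes will be analysed by the same approach, which can be read as extending the mixed model beyond the three outcomes it names. This stands, and it rules out saying that no physical measure is taken in both arms. It does not close the gap: the measure is self-reported function, it is classed as quality of life (an Aim 1 outcome in Section 4), and nothing names it as the fitness outcome.

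A reader might go further and infer that the fitness part of Aim 2 cannot be answered at all. The documents do not support that. Sections 8 and 14 leave open that usual care used the technology during the trial. Fitness tests are mentioned, though undefined. The intake and follow-up questionnaires are attachments that are not in the public documents, so activity items in them cannot be excluded. For the same reason it is an inference, not a stated fact, that the paired tests use the intervention arm alone.

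It is also fair to say that the SAP does not tie the step tests to Aim 2 or call them evidence of program effect. The risk of misreading is therefore a possibility and not something the plan commits to. But these tests are the only activity analysis in the plan, and nothing labels them as descriptive.

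**Conclusion.** The point holds in this form: the fitness part of Aim 2 has no designated outcome, and the plan as written does not test it with a randomised contrast. In size, 0 of the 3 step comparisons has an arm term, and 0 measures in the endpoint list or schedule table are step, activity or performance-fitness measures. The nearest substitute is the t-test of change in PROMIS Physical Function.

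This conclusion rests on the listed endpoints and the named analyses, and it does not depend on who wears a sensor. The absence of step data in usual care is likely under Section 9 but not settled. The percentages in the illustration depend on the assumed common rise in steps; they show how the test behaves and do not predict this trial.

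**What to change.** 1. **Reconcile the sensor text.** Bring Section 9 into line with Sections 8 and 14, and state which arms supplied step data during follow-up and at which weeks.
2. **If both arms supply concurrent steps:** replace the paired t-tests with a between-arm comparison of steps in the group-by-time mixed model. State when week counting starts: randomisation follows consent immediately, so if weeks run from enrolment, the Week 2 baseline is a post-randomisation value.
3. **If only the intervention arm does:** restate Aim 2's randomised comparison in terms of measures taken in both arms, namely the clinical indicators and PROMIS Physical Function. Name both explicitly in the group-by-time mixed model.
4. **In either case:** label any within-person step analysis as descriptive, and not as a test of Aim 2 or as evidence of program effect. Define the fitness tests mentioned in Section 8, or delete the reference.

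The cost is wording in the protocol and SAP plus a few explicitly named models on data already collected. If usual care has no step data, the claim narrows from fitness to self-reported physical function.
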